The first choice of rescue therapy should be the adjustment of insulin therapy. Its dosage will be left to the discretion of the investigator. In very rare cases, adjustment of background therapy or addition of another oral anti-diabetic medication would be appropriate. Such cases should be discussed with the local clinical monitor or the Trial Clinical Monitor (TCM). Rescue therapy should be taken in accordance with the local prescribing information of the respective drug, taking into account potential contraindications.

The following permitted antidiabetic therapy will be considered to be rescue therapy:

- **For patients with a baseline daily insulin dose ≤ 10 units, any increase of insulin >50% from baseline for > 7 days duration**
- **For patients with a baseline daily insulin dose >10 and ≤ 20 units, any increase of insulin >30% from baseline for > 7 days duration**
- **For patients with a baseline daily insulin dose > 20 units, any increase of insulin >20% from baseline for > 7 days duration**
- **Any increase in metformin for ≥ 1 day**
- **Any introduction of a new antidiabetic therapy for ≥ 1 day.**

A FPG, HbA_{1c} sample should be taken before initiation of rescue therapy and sent to central lab for analysis. The HbA_{1c} sample is not required if a sample has been taken and sent to the central lab for analysis within the last 4 weeks.

Hypoglycaemia

If the patient is experiencing hypoglycaemia (criteria see [section 5.3.7](#)), the investigator should review the diary responses to diet and physical activity as well as the HBGM results to determine the appropriate approach to reduce occurrences of hypoglycaemia (e.g., encouraging the patient not to skip meals, increasing carbohydrate intake if increasing exercise, decreasing or adjusting the patient's permitted antidiabetic therapy).

In the case of hypoglycaemia that may put patient on risk (e.g. repeated symptomatic hypoglycaemia or severe hypoglycaemia), appropriate adjustment of anti-diabetic therapy such as a dose reduction / discontinuation of ongoing rescue medication or existing background therapy should be initiated. Reduction or discontinuation of ongoing rescue medication should be considered before a reduction in the dose of existing background therapy.

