5.2 ASSESSMENT OF EFFICACY

HbA_{1c}

Blood samples for the determination of HbA_{1c} will be taken at all visits except Visit 2. The blood sample can be taken at any time during the visit. For the determination of HbA_{1c}, 3 mL of blood will be collected. The samples will be analysed at a central laboratory or its affiliates having a National Glycohemoglobin Standardization Program (NGSP) Level I certificate. Further details about sample handling, shipment, and assay procedures can be found in the Investigator's Site File (Lab manual).

Fasting plasma glucose (FPG)

Blood samples for the determination of FPG at the central laboratory will be taken after an overnight fast. The samples should be taken before breakfast and before trial drug administration. The samples will be measured at a central laboratory using validated assays. Further details about sample handling and shipment can be found in the ISF (Lab manual).

Meal Tolerance Test (MTT)

Meal Tolerance Test (MTT) will be performed using a standardised breakfast. MTT at Visit 3 would be performed before randomisation, i.e. without intake of trial medication during the MTT.

At Visit 3, after blood sample of FPG drawing, patients would have a standardised breakfast and intake metformin and/ or accepted pre-mixed insulin (if applicable), finished within 15 min, and PPG blood samples would be collected at time points 60 ±10 min and 120 ±10 min after the start of standardised breakfast. Study medication would only be taken after last PPG blood samples drawing, i.e. following randomisation.

At Visit 8, 30 min after blood sample of FPG drawing and administration of study medication, patients would have a standardised breakfast and intake metformin and/ or accepted pre-mixed insulin (if applicable), finished within 15 min, and PPG blood samples would be collected at time points 60 ±10 min and 120 ±10 min after the start of standardised breakfast.

Weight and Waist circumference

Weight measurements should always be done on the same scales for one patient. In order to get comparable body weight values, it should be performed in the following way:

- fasting (except for the screening visit),

- after the urine sampling (weight after bladder voiding),
- shoes and coat/jackets should be taken off
- pockets should be emptied of heavy objects (i.e. keys, coins etc)

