7.3 PLANNED ANALYSES

The statistical analysis will be based on the following populations.

Treated Set

The treated set (TS) will consist of all patients who were randomised and treated with at least one dose of study drug.

Full Analysis Set

The full analysis set (FAS) will consist of all patients in the TS who had a baseline and at least one on-treatment HbA_{1c} measurement.

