7.3.1 Primary endpoint analyses

The primary analysis will be performed on the FAS and patients will be assigned to the treatment they were randomised to. A REML-based MMRM approach is applied to compare the change in HbA_{1c} from baseline after 24 weeks of treatment ([Section 7.2](#)).

The statistical model will be

HbA_{1c} change from baseline = overall mean + baseline HbA_{1c} + treatment + type of insulin
+ week+ week by treatment interaction
+ baseline HbA_{1c} by week interaction
+ random error

This model includes effects accounting for the following sources of variation: ‘baseline HbA_{1c}’, ‘treatment’, ‘type of insulin (basal insulin or any permitted pre-mixed insulin)’, ‘week’, ‘week by treatment interaction’ and ‘baseline HbA_{1c} by week interaction’. ‘Treatment’, ‘type of insulin’, ‘week’ and ‘week by treatment interaction’ are fixed, categorical effects, and ‘baseline HbA_{1c}’ and ‘baseline HbA_{1c} by week interaction’ are continuous, linear covariates. For each patient, the error terms from the on-treatment visits represent the within-patient variability, and are assumed to follow a multivariate normal distribution with an unstructured covariance matrix.

If the model fails to converge, further covariance structures will be tested, details will be provided in the TSAP. The first model to converge will be used as the primary analysis. The Kenward-Roger approximation will be used to estimate the denominator degrees of freedom. Significance tests will be based on least squares means using a two-sided $\alpha=0.05$ (two sided 95% confidence intervals).

Only the available data which were observed whilst patients were on treatment will be included in the analysis. Missing data are handled implicitly by the above statistical model,

rather than by using any imputation. This approach, referred to as observed case (OC), will additionally set to missing all values measured after rescue medication use.

Superiority will be tested using the p-value of the treatment effect and a two-sided 95% confidence interval for the treatment difference.

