7.5 HANDLING OF MISSING DATA

In the primary analysis, missing data will not be imputed (OC approach). The mixed effect model will handle missing data based on a likelihood method under the “missing at random” assumption.

If rescue therapy is initiated, HbA_{1c} and FPG values after rescue medication will be set to missing and the missing data will be handled as above (OC approach), according to the analysis strategy. For the analysis of secondary endpoints using ANCOVA, missing values will not be imputed (OC approach).

For binary endpoints including an HbA_{1c} response criterion, non-completers’ considered failure (NCF) will be applied, i.e., patients who discontinued from the trial prematurely and have no HbA_{1c} measurement at Week 24 will be considered as non-responders.

Methods to handle any other exceptional cases will be considered before unblinding the data and will be applied in a manner consistent with other trials of this type. The evaluability of patients with deviations from the protocol likely to confound the treatment response will be decided prior to unblinding.

With respect to safety evaluations, it is not planned to impute missing values. The handling of missing biomarkers will be specified in the TSAP.

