6.6 HANDLING OF MISSING DATA AND OUTLIERS

Based on the different reasons of patients' data missing for different endpoints, various methods will be used to assess the impact of missing data on the efficacy endpoints of this trial, depending upon the type of the endpoint. A description of the various approaches are given in the following:

Observed cases (OC)

One general approach that is possible for all endpoints is to analyse only the available data that were observed while patients were on treatment, i.e. excluding the missing data. Missing data in this analysis will not be replaced.

For all efficacy endpoints, this OC-technique will be adapted by setting any values taken after rescue medication to missing. The definition of rescue therapy please refers to [section 5.3](#).

It should be noted that this method provides unbiased estimates only under the assumption that the data are missing at random; and so, this method is likely to lead to anti-conservative estimates of the treatment effects in case of data missing due to patients dropping-out because of the lack of efficacy of the drug under study. However, since it can be expected that the drop-out rate due to lack of efficacy and the rate of patients with rescue therapy is higher in

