Repeated and unscheduled efficacy measurements will be assigned to the nominal visits and listed in the subject data listings according to the time windows described above. Only one observation per time window will be selected for analysis at an on-treatment visit – the value will be selected which is closest to the protocol planned day. If there are two observations which have the same difference in days to the planned day or if there are two observations on the same day, the earliest value will be used. If an observation is available on the last day of treatment, this observation will be preferably selected over any later observation that is still within the time window. If there are multiple values within the time window of the last visit, including a value on the last day of drug intake, the value on the last day of drug intake is used as the value of the last visit.

Safety measurements will be assigned to the nominal visit as recorded on the eCRF or as provided by the laboratory.

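### The 4-week waiver of the pre-rescue HbA1c sample can leave a patient rescued before Visit 4 with no post-baseline value in the primary analysis

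*Protocol*

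**What the plan says.** **Sampling before rescue.** Under Protocol 4.2.1 (Hyperglycaemia), an FPG and HbA1c "sample should be taken before initiation of rescue therapy and sent to central lab for analysis". The next sentence relaxes this for HbA1c only: it "sample is not required if a sample has been taken and sent to the central lab for analysis within the last 4 weeks". That sentence does not ask for the recent sample to be on treatment.

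**Scheduled HbA1c.** Protocol 5.2 states that samples "will be taken at all visits except Visit 2". Nothing is therefore scheduled between Visit 3 (Week 0) and Visit 4 (Week 4). Protocol 7.1 defines baseline as the last measurement before the first randomised dose, which is normally the Visit 3 sample.

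**Values after rescue.** Protocol 7.3.1 says that the observed-case approach "will additionally set to missing all values measured after rescue medication use". SAP 6.6 says that "this OC-technique will be adapted by setting any values taken after rescue medication to missing". Protocol 7.5 adds that the primary analysis imputes nothing and relies on missing at random.

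**Analysis set and windows.** The FAS is "all patients in the TS who had a baseline and at least one on-treatment" HbA1c measurement (Protocol 7.3). In SAP 6.7 the Week 4 window runs from Day 2 to Day 43. "Repeated and unscheduled efficacy measurements will be assigned to the nominal visits", and one value per window is kept, the one closest to the planned day.

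**The concern.** Once rescue starts, later HbA1c values leave the primary analysis. The pre-rescue sample is then the last chance to record the patient's state in the modelled outcome. Missing at random is easier to defend when the worsening that led to rescue is at least partly observed. The waiver drops this sample only in patients who are rescued, so the loss is related to outcome, and SAP 6.6 expects rescue to be more common on placebo.

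The sharpest case is rescue before Visit 4. The only sample from the last 4 weeks is then the baseline, and the patient can be randomised, treated and fail without contributing to the primary comparison. The patient may still be counted in the FAS: SAP 6.7 defines on-treatment by drug intake plus 7 days, and neither document says whether a post-rescue value qualifies a patient. The FAS count could then hide the loss.

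**Working it through.** **1. The plan's own figure.** Inputs from Protocol 7.7: difference 0.55, SD 1.1, 100 per group, two-sided 5%, dropout about 2.2%.

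- SE of the difference = 1.1 × √(2/100) = 0.156.
- Normal approximation: 0.55/0.1556 − 1.96 = 1.58, power 94.2%. The exact noncentral t gives 94.0%. The stated 94% reproduces.
- 100/(1 − 0.022) = 102.2, rounded up to 103 per arm, 206 in total. This also reproduces.

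**2. Rescue before Visit 4.** Take Visit 3 as Day 1 and Visit 4 as Day 29.

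- The baseline sample is at most 28 days old through Day 29, so the waiver is available for any rescue on Days 2 to 28.
- Protocol 4.2.1 gives a rescue criterion from Week 1, so rescue in this period is possible.
- If the waiver is used, there is no on-treatment HbA1c before rescue, and Weeks 4, 8, 12, 18 and 24 are all set to missing: 0 of 5 usable values and no row in the model.
- A sample on any of those days would have fallen in the Week 4 window (Days 2 to 43).
- If Visit 4 is late, the waiver lapses after Day 29.

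**3. Later rescues.** The table lists non-visit days on which the last planned sample is at most 28 days old and the current window holds no earlier sample.

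| Window (SAP Table 6.7: 2) | Last planned sample | Days affected | Count | Patient still in model? |
|---|---|---|---|---|
| Week 4 (2–43) | Day 1 (baseline) | 2–28 | 27 | No |
| Week 8 (44–71) | Day 29 | 44–56 | 13 | Yes |
| Week 12 (72–106) | Day 57 | 72–84 | 13 | Yes |
| Week 18 (107–148) | Day 85 | 107–113 | 7 | Yes |
| Week 24 (from 149) | Day 127 | 149–155 | 7 | Yes |

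The total is 67 of the 167 days from Day 2 to Day 168 (40%). Total loss is confined to 27 of 167 (16%).

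**4. Shift in an arm's mean.** If a share p of an arm is omitted and those patients are d points worse than the rest, the mean moves by p × d. The documents give neither p nor d. Assume d = 1.0 and 1 to 3 of 103 placebo patients (about 1% to 3%). The shift is then 0.01 to 0.03 points, which is 0.06 to 0.19 of the SE (0.156) and 1.8% to 5.5% of the 0.55 difference.

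**5. Numbers and power.** Contributors = 206 × (1 − 0.022 − r), where r is the assumed share of all patients lost this way. Power is from the t-test.

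| r | Contributors | Per arm | Power |
|---|---|---|---|
| 0% | 201.5 | 100.7 | 94.2% |
| 1% | 199.4 | 99.7 | 94.0% |
| 2% | 197.3 | 98.7 | 93.8% |
| 5% | 191.2 | 95.6 | 93.0% |
| 10% | 180.9 | 90.4 | 91.7% |

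The margin over the required 200 is 1.5 patients, so two such losses use it up. Power barely changes.

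**6. Order of selection.** Suppose a pre-rescue sample on Day 10 and a Visit 4 sample on Day 29, after rescue. Both lie in the Week 4 window, and Day 29 is the planned day. If selection comes first, Day 29 is picked and then set to missing, and the Day 10 value is lost. If exclusion comes first, Day 10 is used. SAP 6.7 and Table 6.6: 1 do not state the order.

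**The case against.** The case against giving this much weight is strong, and most of it stands.

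- **Direction.** SAP 6.6 acknowledges the dependence on missing at random. It argues that, with more lack-of-efficacy dropout and rescue on placebo, the placebo-adjusted effect is estimated conservatively. A reader might infer that the waiver flatters linagliptin. The documents do not support that: losing poor placebo outcomes shrinks the difference.
- **Early rescue is filtered.** Exclusion criterion 1 removes confirmed fasting glucose above 240 mg/dL in run-in. The rescue criterion up to Visit 6 uses the same level, needs home-monitoring support and must be confirmed on another day. An insulin increase counts as rescue only above 20% to 50% of baseline (by baseline dose) for more than 7 days. Cases may be few, though a patient just under the threshold at randomisation can still cross it.
- **An early HbA1c says little.** Protocol 3.2 describes HbA1c as reflecting the preceding 12 weeks, so a sample in the first weeks mostly shows the period before randomisation. It would put the patient in the model but would not recover a Week 24 outcome.
- **The 40%.** A reader might take 67 of 167 days to mean that 40% of rescues are affected. It is a share of calendar days, not of patients or rescues, and 40 of the 67 days concern patients who stay in the model.
- **The waiver is permissive.** A reader might infer that every early rescue drops out. The text only makes the sample optional, and a site may still take it.

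These points limit the size and direction of the effect. They do not remove the gap.

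**Conclusion.** The gap is real and narrow. At a site that uses the waiver, a patient rescued before the Visit 4 sample has no usable post-baseline HbA1c and no row in the primary model. Some later rescues lose the value for the current window only.

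The likely effect is small: about 0.01 points per 1% of an arm omitted, assuming those patients are 1.0 point worse than the rest. The amount an early sample would restore is smaller still. Power stays at 91.7% or more even if 10% of patients were lost this way. The early-rescue rate is not in the documents, so all of these sizes rest on assumption. If placebo failures predominate, the bias works against linagliptin.

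This does not threaten the primary conclusion. It is an avoidable, outcome-related loss of data that is cheap to close. Minor priority.

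**What to change.** **Protocol 4.2.1.** Delete the 4-week waiver and draw the HbA1c tube with the pre-rescue FPG that is already required. At minimum, let the waiver apply only when the sample from the last 4 weeks was taken after the first randomised dose. The minimum version closes the no-row gap but leaves the later empty windows.

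**SAP 6.7.** Add one line: post-rescue values are excluded before the single value per window is selected. Without it, a pre-rescue sample can be displaced by a post-rescue visit value that is then set to missing. A reader might infer that the window rules already protect the extra sample, but the text does not fix the order.

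**Cost.** One extra 3 mL tube for rescued patients, at a draw that already takes place, and one sentence in each document. Rescue criteria and treatment are unchanged.

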4.2.2 Restrictions

4.2.2.1 Restrictions regarding concomitant treatment

Short-term use of additional prandial/intravenous insulin will be permitted (only in the event of an emergency situation and/or hospitalisation) based on clinical judgement of the Investigator or treating physician. Prolongation of additional prandial/intravenous insulin treatment over more than 2 weeks vs. treatment discontinuation should be discussed on a case-by-case basis between the Investigator and the CML/TCM. Please also refer to [Section 3.3.3](#) regarding the permitted use of antidiabetic agents pre-trial.

Additionally, treatment with anti-obesity drugs, herbal medications with antidiabetic effects or systemic steroids will be prohibited due to their influence on glucose metabolism. However, one off or short-term use (i.e. ≤ 1 week's duration) of systemic steroids will be

permitted as well as therapy with non-systemic steroids such as inhaled or local steroids. Furthermore, for patients taking thyroid hormones, any change in the dose should be avoided. If dose changes do occur, then they should be recorded in the source documents and in the eCRF.

For patients receiving metformin, in case a vascular administration of iodine containing contrast agent is required, metformin should be temporarily discontinued at the time of or before the contrast agent is given and resumed not earlier than 48 hours after administration.

4.2.2.2 Restrictions on diet and life style

At the beginning of the Run-in period, patients will receive diet and exercise counselling by a diet specialist or delegated staff member. The counselling will be based on local diet recommendations. The patients will be reminded to follow the agreed diet and exercise plan at every visit.

Patients also should not take part in another clinical trial involving an investigational medicinal product within 2 months prior to informed consent.

4.2.2.3 Restrictions regarding women of childbearing potential

Women of childbearing potential must use the contraception methods described in the patient information.

4.3 TREATMENT COMPLIANCE

Patients are requested to bring all remaining trial medication including empty package material with them when attending visits. The tablets will be counted by the investigator or designee and compliance will be calculated in a worksheet, which must be kept as a source document.

Based on tablets counts, treatment compliance will be calculated as the number of tablets taken, divided by the number of tablets which should have been taken according to the scheduled period, multiplied by 100. Compliance will be verified by the on-site monitor authorised by the sponsor.

$$\text{Treatment compliance (\%)} = \frac{\text{Number of tablets actually taken} \times 100}{\text{Number of tablets which should have been taken}}$$

Compliance during the placebo run-in period should be between 80% and 120%. If compliance is outside this range, the patient should be carefully interviewed and, if necessary, re-informed about the purpose and the conduct of the trial. Unreliable patients should not be randomised at the discretion of the Investigator.

Compliance during the double-blind treatment period should also be between 80% and 120%. Patients who are not compliant according to this definition should be carefully interviewed and re-informed about the purpose and the conduct of the trial.

5. VARIABLES AND THEIR ASSESSMENT

5.1 TRIAL ENDPOINTS

5.1.1 Primary Endpoint

The primary endpoint in this study is the change from baseline in HbA_{1c} after 24 weeks of treatment. Throughout the study protocol, the term "baseline" refers to the last observation prior to the randomised period.

5.1.2 Secondary Endpoints

Secondary efficacy endpoints are:

- Change from baseline in FPG after 24 weeks of treatment;
- Change from baseline in 2-hour PPG after 24 weeks of treatment
- Proportion of patients with HbA_{1c} on treatment <7.0% after 24 weeks of treatment
- Proportion of patients with HbA_{1c} on treatment <6.5% after 24 weeks of treatment
- Proportion of patients with HbA_{1c} lowering by at least 0.5% after 24 weeks of treatment

Secondary safety endpoints are:

- Incidence of investigator-reported hypoglycaemic events confirmed by a measured blood glucose ≤ 70 mg/dL (≤ 3.9 mmol/L)
- Incidence of severe hypoglycaemic events (requiring active assistance by another person, or fatal)

5.2 ASSESSMENT OF EFFICACY

HbA_{1c}

Blood samples for the determination of HbA_{1c} will be taken at all visits except Visit 2. The blood sample can be taken at any time during the visit. For the determination of HbA_{1c}, 3 mL of blood will be collected. The samples will be analysed at a central laboratory or its affiliates having a National Glycohemoglobin Standardization Program (NGSP) Level I certificate. Further details about sample handling, shipment, and assay procedures can be found in the Investigator's Site File (Lab manual).

Fasting plasma glucose (FPG)

Blood samples for the determination of FPG at the central laboratory will be taken after an overnight fast. The samples should be taken before breakfast and before trial drug administration. The samples will be measured at a central laboratory using validated assays. Further details about sample handling and shipment can be found in the ISF (Lab manual).

Meal Tolerance Test (MTT)

Meal Tolerance Test (MTT) will be performed using a standardised breakfast. MTT at Visit 3 would be performed before randomisation, i.e. without intake of trial medication during the MTT.

At Visit 3, after blood sample of FPG drawing, patients would have a standardised breakfast and intake metformin and/ or accepted pre-mixed insulin (if applicable), finished within 15 min, and PPG blood samples would be collected at time points 60 ±10 min and 120 ±10 min after the start of standardised breakfast. Study medication would only be taken after last PPG blood samples drawing, i.e. following randomisation.

At Visit 8, 30 min after blood sample of FPG drawing and administration of study medication, patients would have a standardised breakfast and intake metformin and/ or accepted pre-mixed insulin (if applicable), finished within 15 min, and PPG blood samples would be collected at time points 60 ±10 min and 120 ±10 min after the start of standardised breakfast.

Weight and Waist circumference

Weight measurements should always be done on the same scales for one patient. In order to get comparable body weight values, it should be performed in the following way:

- fasting (except for the screening visit),

- after the urine sampling (weight after bladder voiding),
- shoes and coat/jackets should be taken off
- pockets should be emptied of heavy objects (i.e. keys, coins etc)

Waist circumference measurements should be made around a patient's bare midriff, after the patient exhales while standing without shoes and with both feet touching and arms hanging freely. The measuring tape should be made of a material that is not easily stretched, such as fibreglass. The tape should be placed perpendicular to the long axis of the body and horizontal to the floor and applied with sufficient tension to conform to the measurement surface.

Waist circumference should be determined by measuring the midpoint between the lowest rib and the iliac crest.

